5.2 Inclusion criteria

All participants of the study must meet the following criteria:

- » Adult patients with advanced malignancies with bone metastases
- » Treatment with ZOLEDRONIC ACID ACTAVIS formulation at least 30 days prior to enrollment

The inclusion of each participant in the study must be separated from the decision on the treatment with ZOLEDRO-NIC ACID ACTAVIS formulation.

5.3 Exclusion criteria

Patients meeting the following criteria will not be included in the study:

- » Patients treated with ZOLEDRONIC ACID ACTAVIS less than 30 days prior to inclusion in the study.
- » Patients diagnosed with chronic kidney disease stage 5 (Creatinine clearance before treatment < 30 mL/min).
- » Hypersensitivity to the active substance, other bisphosphonates or any of the medicinal formulation excipients (mannitol, sodium citrate).

5.4 Procedures associated with the treatment discontinuation or the patient withdrawal from the study

If the patient discontinue participation in the Study, the main reason for exclusion from the study will be recorded in the Observation Form (CRF). Exclusion from the study because of adverse effects will be adequately described.

If the patient discontinue participation in the Study due to an associated adverse event, an investigator should follow the procedures described in Section 9 in order to assess the safety of ZOLEDRONIC ACID ACTAVIS.

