| DESIGN OF THE STUDY: | In the study will participated Oncologist and Urologist proving treatment of patients with advanced malignancies involving bone using ZOLEDRONIC ACID ACTAVIS formulation not less than 30 days prior to enrollment. Observing program will be implemented about 4 months. Data on the safety profile of ZOLEDRONIC ACID ACTAVIS formulation will be recorded in individual observation form (CRF) over two consecutive visits: the starting visit (first -1) and control visit (second -2) at least two months from the date of 1st visit. According to the date of the planned visit arising from clinical needs of the patient. |
| STUDY POPULATION: | Adults patients diagnosed with advanced malignancies involving bone (diagnosis according to ICD-10) in which by clinical indications at least 30 days prior to enrollment started therapy with ZOLEDRONIC ACID ACTAVIS formulation. |
| DRUG ASSESSED IN THE NON-INTERVEN- TIONAL STUDY: | ZOLEDRONIC ACID ACTAVIS 4 mg/5mL concentrate for solution for infusion contains in 1 mL concentrate 0.8 mg zoledronic acid (as monohydrate). It is sterile, clear and colorless concentration for solution for infusion. ZOLEDRONIC ACID ACTAVIS formulation indicated in prevention of skeletal related events (pathological fractures, spinal compression, radiation or surgery to bone, or tumor-induced hypercalcaemia) in adults patients with advanced malignancies involving bone as well as in treatment of adults patients with tumor-induced hypercalcaemia (TIH). |
| ENDPOINTS: | Safety endpoints and methods its evaluation: Collection of information on adverse events related to ZOLEDRONIC ACID ACTAVIS formulation treatment. Serious adverse events should be reported to EUROPHARMA immediately, not later than 24 hours after being informed of the SAE. This report does not relieve the doctor from the notification of adverse events in accordance with Art. 45a of the Act on the profession of doctor and dentist. |
| STATISTICAL METHODS: | A sample size of approximately 3,500 patients was based on the feasibility study. The data analysis obtained in the study will be descriptive: data sets will consist of summary statistics, such as numbers, mean values, standard deviation, median, minimum and maximum values observed frequency/ percentage. The safety analysis will be conducted on the safety population. |
| | |

| Procedures for particular visits | | Visit 2* |
|--|---|----------|
| Demographic data | х | |
| Data on the primary disease | х | |

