3.1.1. Characteristics of the study population

Adult patients of both sexes, who, based on ICD-10 meet the criteria for diagnosis of advanced malignancy involving bone and do not meet the exclusion criteria, as well as treated with ZOLEDRONIC ACID ACTAVIS not less than 30 days prior to enrollment will be included to the study.

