7.1 Safety endpoints and methods of its evaluation

7.1.2. Related adverse events

Data on adverse events related to treatment with **ZOLEDRONIC ACID ACTAVIS** will be collected during the observation period and will also include adverse events occurring before enrolment to the Study. Information on these events will be collected during visits to specialist clinics based on directly asked questions in the survey. Doctors are required to report observed related adverse events to [contact]. For further description on reporting of adverse events please see Section 9.

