9. REPORTING RELATED ADVERSE EVENT

9.1 The division of adverse events

The related adverse events occurring during the treatment with the study drug is each related adverse events that follows during the active phase of the study, if:

» it was not present prior to the first dose of study drug

or

» it was presented before the first dose of study drug administration but its intensity was increased during the non-interventional Study

or

» it was presented before the first dose of study drug administration, its intensity did not changed but during the non-interventional Study found an association between administration of the study drug and the onset of this effect.

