10.4.3. The safety assessment

All safety data will be included in the summaries of data on individual patients. Analysis and summary tables are based on data from the safety population

The related adverse events will be coded in accordance with Medical Dictionary for Regulatory Activities (Med-DRA).

The prevalence of all reported related adverse events and serious adverse events occurring during the study drug administration will be presented in the form of tables. In addition, summary tables will be presented, that will include data on the maximum severity, relationship to the study drug administration and related data on adverse events, and patients who discontinued treatment with study drug for any reason.

The related adverse events occurring during the study will be noted in the tables related to adverse events. Medication usage due to concomitant disease will be summarized with the number and percentage of patients receiving them divided into a group of pharmacological and generic name of the drug.

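### An undated hypersensitivity exclusion and a 30-day minimum, both judged after exposure, undercount early serious reactions by an amount the protocol does not allow to be computed

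*Protocol*

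**What the plan says.** The main aim (Section 2.1) is the safety profile; tolerance is the additional aim (Section 2.2).

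**Time on drug.** The synopsis describes patients who "at least 30 days prior to enrollment started therapy with ZOLEDRONIC ACID ACTAVIS formulation". Section 3.1.1 takes patients "treated with ZOLEDRONIC ACID ACTAVIS not less than 30 days prior to enrollment will be included to the study". Section 5.2 requires "Treatment with ZOLEDRONIC ACID ACTAVIS formulation at least 30 days prior to enrollment", and Section 5.3 repeats the rule as an exclusion: "Patients treated with ZOLEDRONIC ACID ACTAVIS less than 30 days prior to inclusion in the study".

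**Hypersensitivity.** Section 5.3 also excludes "Hypersensitivity to the active substance, other bisphosphonates or any of the medicinal formulation excipients (mannitol, sodium citrate"). No date is attached. The criterion directly above it, on creatinine clearance, is tied to the value before treatment.

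**When eligibility is checked.** The criteria are applied at visit 1 (Sections 6.1 and 6.2.1), after the patient has been treated.

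**Earlier events.** Section 7.1.2 says that the data on related adverse events "will also include adverse events occurring before enrolment to the Study". Section 9.1, however, defines a related event during treatment as "each related adverse events that follows during the active phase of the study", and Section 10.4.3 states: "The related adverse events occurring during the study will be noted in the tables related to adverse events".

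**Analysis set.** Section 10.2 defines the safety population as everyone with at least one dose. Section 10.4 promises event frequencies in the study population.

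**The concern.** Eligibility criteria normally describe a patient before exposure. Here they are applied after it, so a criterion that a reaction to the drug can itself trigger selects on the outcome.

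The undated hypersensitivity exclusion does this directly. Since every candidate has been treated, exclusion for hypersensitivity to this drug can remove only patients treated despite a known hypersensitivity and patients who became hypersensitive on treatment. The second group is part of what the study sets out to count.

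The 30-day minimum does it indirectly. A patient who died of an early reaction cannot enter, and one who stopped or left the clinic because of a reaction is less likely to be seen at a later routine visit.

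Both effects lower the reported frequency of early serious reactions, which favours the product. More patients would not help, because the loss happens at entry.

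**Working it through.** The 3,500 was set by practical limits (Section 10.3), so there is no sample-size calculation to reproduce. The check has four steps.

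**1. Hypersensitivity.** Inputs: N = 3,500 (Section 10.3); listed frequency 1/1000 to below 1/100 (adverse reaction list in Section 1.2). Expected cases at any time on treatment = N × p:

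- 3,500 × 0.001 = 3.5
- 3,500 × 0.01 = 35

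If a share q of these arises before enrolment, the literal rule bars N × p × q of them. The protocol gives no q. For assumed values:

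| q | at 1/1000 | at 1/100 |
|---|---|---|
| 0.25 | 3.5 × 0.25 = 0.9 | 35 × 0.25 = 8.8 |
| 0.50 | 1.8 | 17.5 |
| 0.75 | 2.6 | 26.3 |

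Cases after enrolment are still counted.

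**2. Other early reactions.** Let p be the true risk of an early reaction and d the share of affected patients lost before enrolment, with no loss among the unaffected. The rate seen among enrolled patients is p(1 − d)/(1 − p·d). Both p and d are assumptions. With p = 1%, 35 cases are expected in 3,500 without loss:

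| d | expected cases among 3,500 enrolled |
|---|---|
| 0 | 35.0 |
| 0.10 | 31.5 |
| 0.25 | 26.3 |
| 0.50 | 17.6 |
| 0.75 | 8.8 |

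If 2% of unaffected patients also leave, the rate is p(1 − d)/[p(1 − d) + (1 − p) × 0.98]. With p = 10%:

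- d = 0.50: 0.050/0.932 = 5.4%
- d = 0.30: 0.070/0.952 = 7.4%
- d = 0.20: 0.080/0.962 = 8.3%
- d = 0.05: 0.095/0.977 = 9.7%
- d = 0.02: 0.098/0.980 = 10.0%, which is no bias

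The direction follows once affected patients leave more often than unaffected ones. The size cannot be derived from the protocol.

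**3. Who is lost under the 30-day rule.**

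- Died before day 30: certainly lost.
- Stopped or switched before day 30: unclear. The synopsis asks only that therapy was started, and no criterion requires that it continue. Section 6.2.1 describes all patients as using the drug, which points to current users.
- Had a reaction, not hypersensitivity, and still attends: may enter.

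No section counts patients who started but did not enter. The safety population in Section 10.2 can in practice contain only enrolled patients.

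**4. Whether recalled events reach the tables.** Section 7.1.2 brings pre-enrolment events in. Section 9.1 ties related events to an active study phase, which it does not define. Section 10.4.3 is divided: one sentence tabulates all reported events during drug administration, which would admit them, while another refers only to events during the study. The fate of a recalled early event is therefore not settled.

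**The case against.** The strongest reply is that the protocol excludes nobody for an early reaction other than hypersensitivity. A patient with fever, hypocalcaemia or a creatinine rise after the first infusion can enrol once 30 days have passed; visit 1 takes a history of treatment, adverse events and tolerance, and Section 7.1.2 asks for events before enrolment. This stands. A reader might infer that patients harmed early never enter, but the text does not support that.

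A reader might also infer that tolerance is measured only in patients who tolerated the drug for 30 days. That does not follow either. The criterion is elapsed time, and with infusions every 3 to 4 weeks (Section 1.2) it can be met after one or two of them.

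Nor do the 3.5 to 35 cases all disappear. That is the total at any time, only the pre-enrolment part is barred, and only if investigators apply the exclusion to reactions caused by the study drug.

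Finally, the study is descriptive, and Section 10.3 disclaims definitive safety conclusions. That disclaimer is drawn from the non-statistical sample size. It says nothing about who is missing, and Section 10.4 still promises frequencies. Enrolling established users is a legitimate design choice; leaving the resulting selection uncounted and undisclosed is the weakness.

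**Conclusion.** The concern holds in a limited form. As worded, the hypersensitivity exclusion bars patients who developed a listed reaction to the study drug before enrolment. The 30-day minimum certainly loses patients who died before day 30 and probably loses those who stopped or left the clinic early. Recall at visit 1 repairs this only for patients who enrol, and the sections on what is tabulated do not agree.

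Early serious reactions are therefore undercounted. For hypersensitivity, the ceiling is the pre-enrolment share of 3.5 to 35 cases, and that share is unknown. For other reactions, the figures above are illustrations on assumed loss rates, ranging from no bias to a large one. No figure stated in the protocol is shown to be wrong. The conclusion rests on a literal reading of Section 5.3 and on affected patients being lost more often than unaffected ones.

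**What to change.** 1. In Section 5.3, limit the hypersensitivity exclusion to hypersensitivity known before the first dose of the study drug. This concerns entry into data collection only, not treatment.
2. State in the synopsis and Sections 3.1.1 and 5.2 that patients who started at least 30 days earlier and have since stopped are eligible, and align Section 6.2.1.
3. Record the date of first dose on the Observation Form. Have each centre list, from existing records, the number of patients started and the number not entered, with reasons (death, stopped, reaction).
4. Reconcile Sections 7.1.2, 9.1 and 10.4.3 so that related events before enrolment are tabulated, separately from those on study.
5. Limit the stated frequencies and tolerance results to patients who reached day 30 after starting treatment.

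Opening entry from the first infusion is an alternative. Deleting the 30-day rule alone would not remove the selection, because physicians could still choose established users. It would need consecutive enrolment and matching changes in the synopsis and Sections 3.1.1, 5.2 and 5.3.

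The cost is a few reworded sentences, one date on the form, a small centre-level listing and possibly less favourable frequencies. No patient procedure is added, so the study stays non-interventional. The changes belong before enrolment, since patients who never enter cannot be recovered from the Observation Forms.

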6. METHODOLOGY

6.1 Schedule of the study

Summary of observations and assessments in the implementation of this study are presented in the following table.

Table1. Schedule of the project

| Procedures for particular visits | Visit 1 | Visit 2* |
|--|---------|----------|
| Demographic data | Х | |
| Data on the primary disease | Х | |
| Qualification of patient to the non-interventional study (inclusion criteria) | Х | |
| History concerning the treatment of the primary disease before the administration of ZOLEDRONIC ACID ACTAVIS formulation | Х | |
| History concerning comorbidities and its treatment | Х | Х |
| History concerning course of treatment and the occurrence of possible adverse events of ZOLE- DRONIC ACID ACTAVIS formulation | Х | Х |
| History concerning tolerance of ZOLEDRONIC ACID ACTAVIS formulation in patient opinion | Х | Х |
| Recording of any changes in the drugs used in comorbidities therapy during treatment with ZOLE- DRONIC ACID ACTAVIS formulation | Х | Х |

* This visit will take place only if it is planned as a part of routine observation of the patient.

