In multiple myeloma patients, the risk of renal dysfunction may be increased when Zoledronic acid Actavis is used in combination with thalidomide.

Caution is advised when Zoledronic acid Actavis is administered with anti-angiogenic medicinal products, as an increase in the incidence of osteonecrosis of the jaw (ONJ) has been observed in patients treated concomitantly with these medicinal products.

The adverse events related to use of **ZOLEDRONIC ACID ACTAVIS** formulation, including: (Summary of Product Characteristics, Zoledronic acid Actavis 4 mg/5 ml concentrate for solution for infusion, dated 08-01-2015, EMEA/H/C/002488)

Very common (≥1/10): hypophosphataemia

Common (≥1/100 to <1/10): anaemia, headache, conjunctivitis, nausea, vomiting, decreased appetite, bone pain, myalgia, arthralgia, generalised pain, renal impairment, fever, flu-like syndrome (including fatigue, rigors, malaise and flushing), blood creatinine and blood urea increased, hypocalcaemia

Uncommon (≥1/1000 to <1/100): thrombocytopenia, leukopenia, hypersensitivity reaction, anxiety, sleep disturbance, dizziness, paraesthesia, dysgeusia, hypoaesthesia, hyperaesthesia, tremor, somnolence, blurred vision, scleritis, orbital inflammation, hypertension, hypotension, arterial fibrillation, hypotension leading to syncope and circulatory collapse, dyspnoea, cough, bronchoconstriction, diarrhoea, constipation, abdominal pain, dyspepsia, stomatitis, dry mouth, pruritus, rash (including erythematous and macular rash), increased sweating, muscle spasms, osteonecrosis of the jaw, acute renal failure, haematuria, proteinuria, asthenia, peripheral oedema, injections site reactions (including pain, irritation, swelling, induration), chest pain, weight increase, anaphylactic reaction/shock, urticaria, hypomagnesaemia, hypokalaemia

Rare (≥ 10 000 to <1/1 000): pancytopenia, angioneurotic oedema, confusion, uveitis, bradycardia, cardiac arrhythmia (secondary to hypocalcaemia), interstitial lung disease, arthritis and joint swelling as a symptom of acute phase reaction, hyperkalaemia, hypernatraemia, atypical subtrochanteric and diaphyseal femoral fractures

Very rare (< 10 000): Convulsions, hypoaesthesia and tetany (secondary to hypocalcaemia) episcleritis

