6.2 Visits to a specialist clinic under the study

6.2.1 Screening visit (day 0, visit 1)

All patients will use ZOLEDRONIC ACID ACTAVIS in accordance with the decision of the treating physician and in accordance with the conditions contained in the Summary of Product Characteristics. In the Observation Form the following information will be recorded:

- » patient number
- » patient initials
- demographic data
- » data on primary disease
- » data on treatment with ZOLEDRONIC ACID ACTAVIS
- » concomitant diseases on the basis of medical history
- » data on pharmacotherapy of concomitant diseases
- » determination of the inclusion and exclusion criteria
- » data on tolerance of treatment with ZOLEDRONIC ACID ACTAVIS in opinion of the patient
- » data on adverse events related to treatment with **ZOLEDRONIC ACID ACTAVIS**.

6.2.2 Control visit 2 at least two months from the date of 1st visit according to the date of the planned visit arising from clinical needs of the patient

Patients will be reported on visits to the center for a set period of time. These visits will be conducted in accordance with the plan as part of routine follow-up of the Patient and time set according to the individual clinical needs. During these visits, the Investigators will collect and recorded in the Observation Form (CRF) information on the current course of the primary disease, its current treatment, adverse events related to treatment with ZOLEDRONIC ACID ACTAVIS, potential changes of pharmacotherapy used in primary disease and concomitant disease treatment and assessment of tolerance treatment with ZOLEDRONIC ACID ACTAVIS in the opinion of the patient.

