8.3 Concomitant medication

Data on other drugs used concomitantly with **ZOLEDRONIC ACID ACTAVIS** will be recorded in the Observation Form on every visit.

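### The protocol contradicts itself on whether anticancer drugs given alongside zoledronic acid are recorded, and its stated medication summary leaves them out

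*Protocol*

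**What the plan says.** Section 6.1, Table 1 (the synopsis table has the same rows) deals with other drugs in three places.

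- Cancer treatment is asked for at Visit 1 only, as "History concerning the treatment of the primary disease before the administration of ZOLEDRONIC ACID ACTAVIS formulation".
- Comorbidities and their treatment are asked for at both visits.
- Changes on treatment are asked for at both visits, but the row reads "Recording of any changes in the drugs used in comorbidities therapy during treatment with" the study drug.

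The Visit 1 list in section 6.2.1 has "data on pharmacotherapy of concomitant diseases" and a general item on the primary disease that does not mention its treatment.

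Two other sections ask for more. Section 6.2.2 has the Visit 2 form record the current treatment of the primary disease and, separately, "potential changes of pharmacotherapy used in primary disease and concomitant disease treatment". Section 8.3 on concomitant medication (the second section with that number) says: "Data on other drugs used concomitantly with" zoledronic acid go on the form at every visit. It does not restrict them to comorbidity drugs.

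For the analysis, section 10.4.3 states: "Medication usage due to concomitant disease will be summarized with the number and percentage of patients receiving them". It names no other medication summary.

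Section 1.2 gives the reason to care about anticancer drugs. In multiple myeloma, "the risk of renal dysfunction may be increased when Zoledronic acid Actavis is used in combination with thalidomide". For anti-angiogenic products, "an increase in the incidence of osteonecrosis of the jaw (ONJ) has been observed in patients treated concomitantly with these medicinal products".

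**The concern.** The main aim is the drug's safety profile in patients with advanced cancer, many of whom can be expected to be on other anticancer treatment. The two risk modifiers named in section 1.2 are of that kind. Several reactions listed there, such as nausea, vomiting, anaemia, leukopenia and renal impairment, could also plausibly come from concurrent anticancer drugs.

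Section 10.4 plans to describe the subpopulation in which each common event was reported. Section 9.1.3 restricts collection to events judged related, so the attribution itself depends on knowing what else the patient received. If the form is built from the schedule, the variable most relevant to both is the one left off. An analysis plan written later cannot recover what the form did not ask for.

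**Working it through.** The plan gives no figure on this point, so there is none to reproduce. The check is a comparison of sections.

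**Step 1. What each section requires on anticancer drugs given during zoledronic acid treatment**

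| Source | Visit 1 | Visit 2 |
|---|---|---|
| Synopsis table and Table 1 | No (cancer treatment before zoledronic acid only) | No (no primary-disease row marked) |
| 6.2.1 list | No explicit item | Not applicable |
| 6.2.2 | Not applicable | Yes (current treatment and changes) |
| 8.3 Concomitant medication | Yes, within a general sentence | Yes, within a general sentence |
| 9.1.3 | Only in reports of related events | Only in reports of related events |
| 10.4.3 summary | Not named | Not named |

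Table 1 and 6.2.2 conflict directly at Visit 2. Table 1 and 6.2.1 are narrower than 8.3 at Visit 1.

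**Step 2. Who depends on which source**

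The footnote to Table 1 makes Visit 2 conditional on routine planning, and section 7.2 allows for a single visit. A patient seen twice is covered by 6.2.2 as well as 8.3. A patient seen once is covered routinely by 8.3 alone. The protocol does not say how many patients will be seen once. With p the unknown proportion, the number is 3,500 × p, where p lies between 0 and 1. Each 10% is 3,500 × 0.10 = 350 patients.

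**Step 3. The interval before Visit 1**

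Patients enter after at least 30 days on the drug (5.2, 5.3), and events before enrolment are collected (7.1.2). Cancer treatment given between the first dose and Visit 1 falls outside Table 1's row on earlier treatment. Section 8.3 may cover it, but does not say whether drugs stopped before the visit count.

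**Step 4. Whether event reports fill the gap**

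The frequency of an event among users of a co-medication is users with the event divided by all users. Reports under 9.1.3 can supply the numerator. The denominator needs co-medication recorded in patients without events too, which only 6.2.2 and 8.3 provide.

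**Step 5. Scale of the events concerned**

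These are the frequency bands in section 1.2 applied to 3,500 patients. They are not a forecast for this study.

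- Osteonecrosis of the jaw (1/1000 to below 1/100): 3,500 × 0.001 = 3.5, up to 3,500 × 0.01 = 35.
- Renal impairment (1/100 to below 1/10): 3,500 × 0.01 = 35, up to 3,500 × 0.10 = 350.

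The bands show that both event types are likely to appear in numbers worth describing. They do not measure how much information would be lost.

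**The case against.** The strongest reply is that the data are already required. Section 8.3 covers every visit, including Visit 1, and is not limited to comorbidity drugs. Section 6.2.2 collects current cancer treatment outright. Section 9.1.3 puts other pharmacotherapy into every related-event report, so the patients with a reported jaw or renal event are those whose co-medication must be given. Table 1 is introduced as a summary, and a summary does not cancel a more specific section. The form itself is not shown. The study is descriptive, and section 10.3 disclaims definitive safety conclusions. Which medication tables are produced is often left to an analysis plan.

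Most of this stands. A reader might infer from Table 1 alone that the named interaction risks cannot be monitored, or that no event could be split by co-medication. The documents do not support that, because 8.3, 6.2.2 and 9.1.3 together ask for the drugs concerned.

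The reply does not remove the contradiction. The schedule and the visit list are what a form designer and an investigator work from, and both omit the item. For patients seen once, the only routine requirement is the general sentence in 8.3, and event reports supply no denominator. An unseen analysis plan may widen 10.4.3, which makes that part secondary, but it cannot settle what was collected. A descriptive study still needs this variable to describe its patients.

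**Conclusion.** The point holds as an internal contradiction about what is recorded. The synopsis table, Table 1 and 6.2.1 do not ask for concurrent anticancer drugs; 6.2.2 and 8.3 do. Such drugs may go uncaptured, chiefly in patients seen once, and they lie outside the medication summary that 10.4.3 states.

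The extent is unknown. It depends on how many patients have only Visit 1 and on whether the form follows the schedule or 8.3, and the protocol settles neither. If the form follows 8.3 in full, nothing is lost at collection and only the narrow summary remains. It should be corrected because the repair is small and the protocol itself names anticancer co-medication as raising risk.

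**What to change.** 1. In the synopsis table and Table 1, add one row marked at both visits: anticancer treatment given during zoledronic acid treatment, with agent or class and start and stop dates, including the interval between the first dose and Visit 1.
2. Add the same item to the 6.2.1 list, so that it agrees with 6.2.2 and 8.3.
3. In 10.4.3, extend the medication summary from drugs for concomitant disease to anticancer drugs.
4. Describe osteonecrosis of the jaw with and without anti-angiogenic co-medication, and renal events with and without thalidomide, giving the number of patients in each group.

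The cost is one row on the form, wording changes in four places (synopsis table, 6.1, 6.2.1 and 10.4.3), and a small amount of data entry per patient from the existing oncology chart. No diagnostic procedure is added and treatment is unaffected, so the study stays non-interventional.
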